1.1.5.4 Papillary Thyroid Carcinoma (PTC)

Thyroid nodules are rare in childhood and adolescence, with a general prevalence of less than 2%; however, they are more frequently malignant than in adults (approximately 20% of cases) ([Corrias, 2010](#)). Thyroid carcinomas have an average incidence of approximately 5 per million in patients under the age of 20 years ([NCI, 2012](#)). Incidence typically increases with age in this time-frame, such that the majority of cases are observed in adolescents 15 to 19 years old (approximately 15 per million) ([NCI, 2012](#)). PTC currently comprises approximately 70% of all diagnoses ([NCI, 2012](#)).

Pediatric PTC usually presents at an advanced stage, but still has excellent prognosis, with a 5-year survival rate of >99% ([NCI, 2012](#)). At presentation, 70% of patients typically have regional nodal involvement, and 10% to 20% may have distant metastasis, with the most common site of metastases being the lungs ([Alessandri, 2000](#)). Conditions known to increase risk of childhood PTC are elevated plasma thyroid stimulating hormone (TSH) concentration, Hashimoto's disease, exposure to radiation, and mutations in RET-oncogene.

BRAF V600E mutations are common in adult PTC, reported at a rate of approximately 50% ([Nikiforova, 2009](#); [Melck, 2010](#)). In pediatric PTC, the proportion of BRAF V600E-positive tumors appears to be slightly lower. In recent publications, BRAF V600E mutations were identified in approximately 20% of cases in patients aged <20 years ([Rosenbaum, 2005](#); [Kumagai, 2004](#)).

1.2 Rationale

1.2.1 Study Rationale

The proposed study is a Phase I/IIa, open-label study to determine the safety, tolerability, and pharmacokinetics of oral dabrafenib in pediatric and adolescent subjects aged ≥ 12 months to less than 18 years of age with advanced BRAF V600 mutation positive advanced solid tumors. As noted above, dabrafenib has demonstrated promising efficacy in adults with BRAF V600 mutation-positive advanced or metastatic melanoma as well as other tumor types with BRAF V600 mutations. For patients with refractory, recurrent gliomas, LCH, melanoma, or PTC, the use of second- and third-line cytotoxic chemotherapies, even in dose-intensive regimens, has

yet to yield significant impact on progression-free survival or overall survival. Recent data identifying BRAF V600 activating mutations in pediatric melanoma, gliomas, LCH, and PTC coupled with the recent development of specific BRAF inhibitors may allow for the development of a new therapeutic opportunity for children, and is the primary rationale for this study.

In addition, BRAF inhibitors such as dabrafenib have a substantially different safety profile than cytotoxic chemotherapeutics and radiation therapy, both of which are employed in standard of care regimens for advanced pediatric solid tumors. Moreover, radiation and cytotoxic therapies can have significant long-term effects on the health and development (both physical and cognitive) of children. The Childhood Cancer Survivors Study, a large cohort study conducted in the United States, found that greater than 40% of survivors of pediatric cancers are burdened with long-term adverse health effects (Hudson, 2002). Specifically, the individual components of current therapy for solid tumors lead to both short and long term morbidities. Surgical resection can lead to loss of function or disfigurement, or in the case of CNS tumors, long term neurologic and cognitive sequelae. Cytotoxic chemotherapeutics, especially when administered in dose- or time-intensive manners, can lead to neutropenia and increased risk of infection, sepsis, and death, cardiac dysfunction (doxorubicin), infertility (cyclophosphamide), renal injury and hearing loss (cisplatin). In addition, many of these cytotoxic agents, in particular, DNA alkylating agents and epipodophyllotoxins, have long been known to predispose patients to treatment-associated leukemias (Hawkins, 1992). Radiotherapy can also have profound effects on skeletal growth and, for patients with CNS tumors, on endocrine function, cognition, vasculopathy and risk of second tumors. New targeted therapeutics such as dabrafenib may offer a way of reducing the need for cytotoxics, or may offer a means by which to reduce dose or exposure, thereby reducing the likelihood of treatment-associated morbidity and mortality.

Given the similarity between adult and pediatric melanoma, data from this study will be used to support a bridging approach to demonstrate that the PK, and (where available) pharmacodynamic and efficacy data in adolescent subjects are similar to that of adults, using a modelling and simulation approach.

In summary, it is thought that dabrafenib has the potential to provide therapeutic benefit to those pediatric patients with advanced solid tumors with BRAF V600 activating mutations. Due to the scarcity of BRAF mutation positive tumors in children, and the anticipated favourable safety profile of dabrafenib in children (based on adult data), enrolment of different pediatric age groups will not be staggered.

1.2.2 Dose Rationale

A maximum tolerated dose (MTD) was not established in adults for dabrafenib in Study BRF112680. However, relationships between the total daily dabrafenib dose and markers of clinical benefit (reduction in FDG-PET uptake and tumor shrinkage) were determined and the PK, safety, pharmacodynamic and efficacy data were used to identify a recommended Phase II dose of 150mg BID. As such, in this pediatric study, dabrafenib dose escalation will proceed to the target geometric mean steady-state plasma exposure observed in adults given the efficacious Phase III dose of dabrafenib 150 mg BID as HPMC capsules. It is not anticipated

that a true MTD will be identified given the low incidence of dose-limiting toxicities (DLTs) seen in the adult clinical development of dabrafenib.

The rationale for this pharmacokinetically-based dose-escalation approach is based on the likelihood that therapeutic benefit in children will be achieved by targeting the adult dabrafenib exposure, principally steady-state AUC(0- τ) following 150 mg BID dabrafenib as HPMC capsules. The geometric mean (95% CI) dabrafenib AUC(0- τ) after administration of 150 mg BID as the HPMC capsule in the Phase III study (BRF113683) was 4341 (3749, 5485) ng*h/mL. These Phase III data were consistent with the preliminary results from the monotherapy arm of study BRF113220 where geometric mean dabrafenib AUC(0- τ) after administration of 150 mg BID as the HPMC capsule was 4648 ng*h/mL. Therefore, the median population target AUC(0- τ) for pediatric subjects will be approximately 4500 ng*h/mL, with the goal of identifying, where possible, a dose for each age grouping (12-18, 6-12, 2-6, and less than 2 years of age) that results in a median dabrafenib AUC(0- τ) that is within the 95% CI for the geometric mean exposure measured in adults in the Phase III study (3749, 5485 ng*h/mL).

The dabrafenib dose selection will be weight-based according to regulatory guidances ([European Medicines Agency, 2006](#); [U.S. Food and Drug Administration, 2000](#)). The recommended adult dose of dabrafenib is 150 mg BID. This dose corresponds to a 3.75 mg/kg total daily dose in an 80 kg adult. The starting dose in Part 1 will be 3 mg/kg total daily dose, approximately 80% of the adult dose adjusted for body weight. Dose escalation in Part 1 will occur in a stepwise manner until the median AUC(0- τ) is greater than approximately 4000 ng*h/mL and does not exceed approximately 5500 ng*h/mL. Dose escalation in Part 1 also will be influenced by the real-time analysis of the safety and other available data obtained during the study.

Based on clinical pharmacology considerations in the pediatric population, the selection of suitable dabrafenib doses for ages 2 to <18 years is not expected to be significantly complicated by developmental factors. However, given the rapidly changing absorption, distribution, metabolism, and excretion processes in children <2 years old, it is difficult to predict the impact of the physiology of infants on dabrafenib exposure. As noted above, since a MTD of dabrafenib was not established in adult subjects with cancer, it is expected that dose-limiting toxicities also will be rare in children. Therefore, a starting dose of 80% of the weight-based dose in adults will provide an adequate safety margin for infants. The total daily dose administered in this study will not exceed 300 mg (150 mg BID).

1.3 Summary of Risk Management

The assessment of the risk of dabrafenib, and suggestions for management of risk, is based on non-clinical data and clinical data from an integrated safety population of 578 adult subjects with melanoma receiving 150 mg dabrafenib BID.

Dermatological effects: Epidermal hyperplasia (acanthosis) and hyperkeratosis of the skin was seen in dogs and in rats. In clinical studies hyperkeratosis (29%), skin lesions including actinic keratosis (7%) and seborrhoeic keratosis (7%), palmar-plantar erythrodysesthesia (PPE) syndrome (13%), rash (18%) and cutaneous squamous cell carcinomas (cuSCC) including keratoacanthomas (KA) (9%) have been observed. Most events were Grade 1 with the exception of cutaneous squamous cell carcinomas, which were predominantly Grade 3.

Dermatological changes are being monitored in subjects through interim medical history, assessment of adverse events and physical examination including examination of the skin. Guidelines on management of hand foot skin reactions (HFSR)/ PPE syndrome and skin rashes have been provided, with stopping criteria for persistent National Cancer Institute Common Terminology Criteria for Adverse Events, version 4.0 (NCI CTCAEv4.0 or higher) NCI-CTCAE Grade 2 or Grade 3 HFSR toxicity. Treatment of SCC, KA and keratotic lesions should occur based upon institutional practice. Dose interruptions or modifications are usually not required for SCC/KA.

Ophthalmology effects: Eye effects including blurred vision (2%), uveitis/iritis (<1%), eye pain (<1%), visual impairment (<1%) and reduced visual acuity (<1%) have been observed in clinical studies to date, with all events Grade 1 or 2. An ophthalmologic consult is required for subjects developing symptoms associated with uveitis including blurry vision, eye pain or erythema.

Pyrexia: In clinical studies, pyrexia was one of the most frequently occurring AEs (27%), most of which (64%) were considered to be related to study treatment. Events were primarily Grade 1 (55%) or Grade 2 (39%) in severity. The majority of events occurred early during study treatment, with a median time to onset of 1st occurrence of 3 weeks, and most cases (74% of first occurrences) were of short duration (≤5 days). The majority of subjects with pyrexia were managed without dose interruption or dose reduction. Across dabrafenib studies, all SAEs of pyrexia, influenza-like illness, cytokine release syndrome, and systemic inflammatory response syndrome underwent clinical review for the identification of serious non-infectious febrile events, with complications of severe rigors, hypotension, dehydration, or renal failure in the absence of another identifiable etiology (i.e., infection). Subjects should be evaluated for signs and symptoms of infection and work up considered as clinically indicated. Dabrafenib must be held for fever of 38.5C or higher, and blood samples for an absolute neutrophil count (ANC) and serum creatinine must be drawn in the setting of fever. Subjects with fever should have a medical evaluation including measurement of blood pressure. Cases of fever with severe rigors or fever with hypotension should be reported as SAEs (regardless of whether or not hospitalization was required).

Acute Renal Failure: Acute renal failure/renal failure has been rarely reported (<1%) in subjects receiving dabrafenib, and a case of granulomatous interstitial nephritis has also been reported in a clinical trial. In some cases complicated pyrexia may be associated with renal insufficiency/renal failure, possibly secondary to dehydration or hypotension. Renal function should be monitored carefully, especially in subjects with pyrexia. Dabrafenib should be interrupted in subjects with significantly elevated serum creatinine (creatinine rise >0.5 mg/dL [44 μmol/L] above baseline or creatinine >2.0 mg/dL [177 μmol/L]).

In juvenile rat studies, dose-dependent effects on kidney (tubular deposits with secondary changes, increased incidence of cortical cysts and tubular basophilia, tubular dilation and reversible increases in serum urea and/or creatinine concentrations) were observed. Renal toxicity has not been observed in adult rats, dogs or mice given dabrafenib for up to 3 months. The spectrum of renal changes noted in juvenile rats suggests obstructive injury. In general, renal toxicity was observed with greater incidence and severity in juvenile rats where dosing was initiated pre-weaning compared to post-weaning. When dosing of dabrafenib was initiated post-weaning (postnatal day 22), there was no progression in the severity of renal findings nor

were there any secondary changes. The observation of greater renal toxicity in rats < 22 days old suggests a higher risk for tubular injury for human infants <1 years of age based on comparison of renal maturation rates, and a correspondingly lower risk for patients between 1 and 4 years of age.

Pancreatitis: Pancreatitis (<1%) and/or increased lipase/amylase (2%) have been reported at a low frequency with dabrafenib, typically occurring within 14 days of starting therapy. For AEs of abdominal pain or suspected pancreatitis, amylase and lipase laboratory samples must be monitored locally.

Hypersensitivity: There has been a report of hypersensitivity (blisters), occurring on the same day as the first dose of study drug as well as upon rechallenge. Grade 1 AEs of blisters on limbs (4 subjects) and drug hypersensitivity (rash, 1 subject) have been reported in previous studies with dabrafenib. However, the precise etiology of these events is unclear.

Embryofetal Development and Reproductive Effects: In embryofetal development studies in rats, developmental toxicities including reduced fetal body weight, embryo-lethality, cardiac ventricular septal defect malformations, delayed skeletal development and variation in thymic shape have been observed. Dabrafenib must not be administered to pregnant women or nursing mothers. Female subjects of childbearing potential are required to use effective methods of contraception from the time of a negative serum pregnancy test within 14 days prior to the first dose of study medication, until 4 weeks after the last dose of study medication. In dogs and in rats, testicular degeneration/depletion has been observed in repeat dose studies (up to 13 weeks duration) with no clear evidence of recovery following off-treatment periods of up to 4 weeks duration. Spermatid retention was observed in mice in a 14 day study. Male subjects enrolled or in follow-up in clinical trials are informed of the potential risk for impaired spermatogenesis, which may be irreversible.

Cardiovascular effects: Data from preclinical studies with dabrafenib suggest the potential for cardiovascular effects, including cardiac valve effects in the 28 day dog study, coronary vascular effects in the 7 day dog study, hepatic vascular effects in a 10 day rat study, increased incidence of minimal cardiomyopathy in male rats and mild increases in heart rate in single dose studies in dogs and rats. In a 13-week oral toxicity study in dogs right atrial wall thickening characterized microscopically by fibrovascular proliferation (transmural granulation tissue) was observed. In the ongoing monotherapy clinical studies, 3 (<1%) non-serious valvular abnormalities meeting stopping criteria have been identified to date; two of these subjects had baseline valvular abnormalities. Additionally, a blinded independent review of available echocardiogram results from subjects participating in the phase 2 BREAK-2 study was performed to further examine the effect of dabrafenib on valvular function. No persistent findings suggestive of a drug effect were observed. Because valvular abnormalities were observed in a minority of subjects in the integrated dabrafenib population, and the results of the central analysis in BREAK-2 were not suggestive of a drug effect, valvular toxicity is no longer considered an AE of special interest for dabrafenib. Subjects with clinically significant baseline cardiac abnormalities are excluded from the study. Safety evaluations include physical examination, 12-lead electrocardiogram (ECG) and echocardiogram (ECHO) monitoring as well as AE reporting.

Respiratory Effects: Lobar bronchoalveolar inflammation has been observed in dogs, with shallow and/or labored breathing noted during the treatment phase in 2 dogs given dabrafenib for 13 weeks. Respiratory changes are being monitored through medical history and physical examination. There have been no corresponding clinical findings identified in clinical trials to date.

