3.7.1 Dabrafenib Intra-Subject Dose Escalation

In certain circumstances in Part 1 of this study, a subject's dose level may be increased up to the highest dose level that is open to enrollment. Only subjects who have completed their DLT assessment period (28 days), who have tolerated treatment, but have measured AUC(0-12) less than target level, may be eligible for escalation. Decisions to increase a subject's current dose will be based on all available data, including safety data and PK data for that subject, and must be agreed by the investigator and the Novartis Medical Lead. Predicted exposure AUC(0-12) at the escalated dose may not exceed 6000 ng*h/mL. Documentation of the dose escalation agreement and predicted exposure must be kept in the study files for the subject.

Dose escalation is only allowed in subjects who are willing to consent to additional PK sampling at the escalated dose level. Additional PK samples will be collected on Day 15 following administration of the escalated dose.

Intra-subject dose escalation will not occur in Part 2.

Subjects will be summarized based on the treatment level to which they were originally assigned.

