3.7.4 Dose Modification Guidelines - Adverse Events of Special Interest

3.7.4.1 Pyrexia

Pyrexia has been observed in adult subjects receiving dabrafenib. In a minority of cases pyrexia was accompanied by symptoms such as severe chills/rigors, dehydration, and hypotension, which in some cases can lead to acute renal insufficiency. Serious non-infectious febrile events have been observed and typically occurred within the first month of therapy.

Subjects should be instructed on the importance of immediately reporting febrile episodes. Therapy with dabrafenib should be interrupted if the patient's temperature is $\geq 38.5^{\circ}\text{C}$ or 101.3° Fahrenheit. In the event of a fever, the subject should be instructed to take anti-pyretics (e.g. ibuprofen or acetaminophen/paracetamol as appropriate to control fever). The use of oral corticosteroids should be considered in those instances in which anti-pyretics are insufficient. In subjects experiencing pyrexia associated with rigors, severe chills, dehydration or hypotension, serum creatinine and other evidence of renal function (e.g. creatinine clearance, BUN) should be monitored carefully during and following severe events of pyrexia. Pyrexia accompanied by hypotension, dehydration requiring intravenous fluids, renal insufficiency and/or severe (\geq Grade 3) rigors/chills in the absence of an obvious infectious cause should be reported as a SAE.

Guidelines regarding management and dose reduction for pyrexia considered to be related to dabrafenib are provided in [Table 3-4](#).

Table 3-4 Mandatory Dose Modification and Recommended Clinical Management for Pyrexia

Occurrence ^{a,b}	Recommended adverse event management guidelines	Mandatory dose modification requirements
Any	
 ● Clinical evaluation for infection and hypersensitivity^c ● Laboratory (local lab) work-up^c ● Hydration as required^d 	
1st Event ^b :	
 ● Administer anti-pyretic treatment as clinically indicated and initiate prophylactic treatment if associated with rigors, renal failure, dehydration, or hypotension^e 	
 ● Interrupt dabrafenib ● Once pyrexia resolves to baseline, restart dabrafenib at the same dose level ● If fever was associated with dehydration, hypotension, or renal insufficiency, reduce dabrafenib to the next lower dose level. ^g

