2nd Event ^e	
 ● Same as for 1st event, and ● Within 3 days of onset of pyrexia 
 ● Optimize anti-pyretic therapy ● Consider oral corticosteroids for at least 5 days or as clinically indicated^f 	
 ● Same as 1st event.
Subsequent Events:	
 ● Within 3 days of onset of pyrexia 
 ● Optimize oral corticosteroid dose as clinically indicated for recalcitrant pyrexia^f ● If corticosteroids have been tapered and pyrexia recurs, restart steroids 	
 ● Interrupt dabrafenib ● Once pyrexia resolves to baseline, restart dabrafenib reduced by one dose level^g

- ^a. Pyrexia is defined as a body temperature equal to or above 38.5°C Celsius or 101.3°F Fahrenheit.
- ^b. For subjects experiencing pyrexia complicated by rigors, severe chills, etc., a clinical evaluation and laboratory work-up is mandatory for each event; anti-pyretic treatment should be started immediately at the first occurrence and prophylactic anti-pyretic treatment is recommended.
- ^c. Thorough clinical examination for signs and symptoms of infection or hypersensitivity is required; laboratory work up should include full blood count, electrolytes, creatinine, BUN, CRP, and liver function tests.
- ^d. Oral hydration should be encouraged in subjects without evidence of dehydration. Intravenous hydration is recommended in subjects experiencing pyrexia complicated by dehydration/hypotension.
- ^e. Anti-pyretic treatment may include acetaminophen (paracetamol), ibuprofen, or suitable anti-pyretic medication according to institutional standards. Prophylactic anti-pyretic treatment may be discontinued after three days in the absence of pyrexia
- ^f. In subjects experiencing pyrexia complicated by rigors, severe chills, etc., which cannot be controlled with anti-pyretic medication, oral corticosteroids should be started at the 2nd event and doses should be gradually increased for subsequent events.
- ^g. Dabrafenib should be reduced by one dose level after 3 episodes of pyrexia complicated by rigors, severe chills etc., which cannot be managed by best supportive care, including increasing doses of oral steroids. Re-escalation of dabrafenib is allowed if no episode of pyrexia is observed in the 4 weeks subsequent to dose reduction

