- During treatment subjects should be monitored as clinically appropriate. Complete blood cell counts should be performed as clinically indicated. Following discontinuation of dabrafenib monitoring for non-cutaneous secondary/recurrent malignancies should continue for up to 6 months or until initiation of another anti-neoplastic therapy, whichever comes first. Any non-cutaneous secondary/recurrent malignancy should be reported as a protocol-specific SAE and treated according to standard clinical practice.
- See [Appendix 6](#) for French country specific guidelines.

Vital Signs

- Vital sign measurements will include systolic and diastolic blood pressure, temperature and pulse rate.
- If a subject develops a fever, refer to Section 3.7.1 for management guidelines.

Electrocardiogram (ECG)

- A single 12-lead ECG will be obtained at each time point during the study using an ECG machine that automatically calculates the heart rate and measures PR, QRS, QT, and

QTcB intervals. Refer to [Section 3.7.4.4](#) for QTcB withdrawal criteria and additional QTcB readings that may be necessary.

Echocardiography (ECHO)

- ECHOs will be performed to assess cardiac ejection fraction. The echocardiographer's evaluation should include an evaluation of left ventricular ejection fraction. Post-dose ECHOs should be compared to baseline to note if there are any changes.
- Copies of all ECHOs and cardiology consultations performed on subjects who experience a >10% absolute decrease in LVEF from baseline and whose cardiac ejection fraction is less than institution's LLN will be required by Novartis for review.

Clinical Laboratory Assessments

Hematology, clinical chemistry and additional parameters to be tested are listed below:

Hematology			
Platelet Count:	Red blood cell (RBC) Indices (at screening and if hemoglobin decrease ≥ 2 g/dL compared to baseline):		Automated White Blood Cell (WBC) Differential:
RBC Count	MCV		Neutrophils
WBC Count (absolute)	MCH		Lymphocytes
Hemoglobin	MCHC		Monocytes
	Reticulocyte Count		Eosinophils
			Basophils
Clinical Chemistry			
BUN	Potassium	AST	Total and direct bilirubin ^a
Creatinine	Chloride	ALT	Uric Acid
Glucose	Total CO ₂	Alkaline phosphatase	Albumin
Sodium	Calcium		Total Protein
Magnesium	Phosphate		
Other tests			
Pregnancy tests			
Amylase and lipase [monitor via local laboratory where appropriate to evaluate certain AEs (i.e., abdominal pain, pancreatitis, etc.)]			

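### Creatinine in fever is compulsory in Protocol Section 1.3 but only recommended in Table 3-4, although mandatory dosing rules need the result; two fever cross-references are also wrong

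*Protocol*

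**What the plan says.** Protocol Section 1.3 (pyrexia paragraph) states that "blood samples for an absolute neutrophil count (ANC) and serum creatinine must be drawn in the setting of fever".

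Section 3.7.4.1, which sites would use to manage a fever, is weaker. Its text on renal monitoring begins "In subjects experiencing pyrexia associated with rigors, severe chills, dehydration or hypotension, serum creatinine and other evidence of renal function", so it is tied to complicated pyrexia. In Table 3-4 the laboratory work-up for any occurrence sits under the column "Recommended adverse event management guidelines". Footnote c requires the clinical examination but only advises the laboratory panel, which names full blood count and creatinine. Footnote b is firm for one group: "For subjects experiencing pyrexia complicated by rigors, severe chills, etc., a clinical evaluation and laboratory work-up is mandatory for each event".

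The mandatory column of the same table, at the first event and by reference at the second, says: "If fever was associated with dehydration, hypotension, or renal insufficiency, reduce dabrafenib to the next lower dose level". Otherwise the drug restarts at the same dose once the fever has resolved.

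Section 6.3 (vital signs) says: "If a subject develops a fever, refer to Section 3.7.1 for management guidelines". That section is headed "3.7.1 Dabrafenib Intra-Subject Dose Escalation". Table 3-5 (renal function) tells sites to treat accompanying pyrexia according to a Table 5. The list of tables has no such number; the pyrexia table is Table 3-4.

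**The concern.** A child can have impaired renal function during a fever without symptoms, and then only a creatinine result shows it. A site that follows Table 3-4 and treats its first column as optional could hold the drug, see the fever settle and restart at the same dose with no creatinine value. With a value, the same table might have required a reduction, or Table 3-5 an interruption or permanent discontinuation. Section 1.3 asks for careful renal monitoring, particularly with pyrexia, and reports kidney effects in juvenile rats that were not seen in adult animals.

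The signposts do not repair this. The procedures section leads to dose escalation, and Section 1.3 introduces its own content as suggestions for managing risk, so a site may not look there for an instruction.

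**Working it through.** No sample size, power or error rate is involved. The check is a comparison of texts, plus simple arithmetic on scale.

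**Step 1. Force of the requirement, by place**

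| Place | Which fevers | Test | Force |
|---|---|---|---|
| Section 1.3 | any | neutrophil count, creatinine | compulsory |
| Section 3.7.4.1 text | complicated or severe | creatinine, other renal measures | advised |
| Table 3-4, any-occurrence row, with footnote c | any | panel with full blood count and creatinine | recommended |
| Table 3-4, footnote b | complicated | laboratory work-up | mandatory |

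The compulsory wording is missing from the working section only for uncomplicated fever. The test is listed there; its force differs, and the neutrophil count is not named.

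**Step 2. Dosing rules that need a creatinine value**

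- Table 3-4, events 1 and 2: reduce if renal insufficiency was present, otherwise restart unchanged.
- Table 3-5, for renal insufficiency considered treatment-related, after a re-check within 24 hours: continue below a 50% rise, interrupt from 50% to below 100%, discontinue permanently at 100% or more. A second occurrence also means permanent discontinuation.
- From event 3, Table 3-4 reduces the dose by one level in any case (qualified by footnote g). The result still matters, because Table 3-5 can require interruption or discontinuation whatever the number of the fever.

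**Step 3. Scale**

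- Children still on treatment: 85 − 52 = 33 (Amendment 11 rationale). The Amendment 10 rationale gives the same 52 with data as of 06-Feb-2019, so 33 is an upper bound.
- All 85 had started by 06-Feb-2019. From then to version 11 (21-Aug-2020) is 562 days, and 562/7 = 80.3 weeks. Every child still treated is past Week 48, when Table 3-9 schedules chemistry and hematology every 12 weeks.
- Chance that a 5-day fever overlaps a scheduled draw: 5/(12 × 7) = 5/84 = 6.0%. Five days is the upper end of the short duration that Section 1.3 gives for most adult first fevers; fever timing is assumed unrelated to visits. Routine tests do not replace a fever draw.
- Scope of the table: "Guidelines regarding management and dose reduction for pyrexia considered to be related to dabrafenib are provided in" Table 3-4. In adults 64% of pyrexia was considered related (Section 1.3). If children are similar, which is an assumption, 100% − 64% = 36% of fevers fall outside the table.

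The number of missed cases cannot be calculated from the documents.

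**The case against.** The strongest reply is that the working section governs and Section 1.3 is out of date. The Amendment 8 rationale says that the safety sections were revised to separate recommended from mandatory procedures, and its log names Section 3.7.4.1. The log also records removal of a neutrophil-count requirement from Section 6.3, with a percentage accepted instead. Section 1.3 still carries fixed creatinine limits (a rise above 0.5 mg/dL, or a value above 2.0 mg/dL), whereas Table 3-5 uses percentage rises. A reader might infer that its compulsory wording settles the matter for both tests in every fever. The documents do not support that for the neutrophil count: no dosing rule in Table 3-4 depends on it, and the Amendment 8 log points the other way.

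For creatinine the reply is weaker. The same log says that adverse event guidance stayed largely as before, and the Amendment 6 pyrexia table listed the work-up for any event without a recommended label. The softer force may come from the new column layout; that is an inference. Whatever the intent, a mandatory rule that turns on renal insufficiency needs a renal result.

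It is also fair that the practical gap is thin. Table 3-4 does list the bloods for any event, the examination is required, and Section 1.3 links renal failure mainly to complicated pyrexia, where the work-up is already mandatory. In adults the median onset of first fever was 3 weeks, long past for these children. This limits the weight of the point but does not make the sections agree.

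**Conclusion.** The point holds for creatinine and for the two cross-references. For the neutrophil count the documents show only that two places disagree; they do not show which is intended.

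The weight is low. It concerns at most 33 children, in fevers that are not complicated, and it touches no endpoint or analysis. A reader might infer that draws have been missed or children wrongly restarted. No document shows this, and Section 1.3 as written already requires the draw. The case for acting rests on two premises: that renal insufficiency can be present without symptoms in an uncomplicated fever, and that some sites work from Table 3-4 rather than Section 1.3. Both are reasonable, and neither can be measured from the documents.

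**What to change.** In the next amendment, with a letter to sites:

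1. Change the fever reference in Section 6.3 to Section 3.7.4.1, and the pyrexia reference in Table 3-5 to Table 3-4.
2. In the Section 3.7.4.1 text, and in the mandatory column of Table 3-4 for any occurrence, require a local serum creatinine at 38.5 °C or higher, with the result available before the restart-or-reduce rule is applied. Placing it in the text as well lets it reach fevers not considered related to dabrafenib.
3. Have the sponsor reconcile the neutrophil-count requirement in Section 1.3 with Amendment 8: either repeat it in Table 3-4 as a blood count with differential, or edit Section 1.3.

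Leave the required examination, the mandatory work-up in complicated pyrexia and the rest of the recommended panel as they are.

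The cost is one small local sample per fever, within the Section 6 limits of 1% of blood volume at one time and 3% in 4 weeks. Waiting for the result is a new condition on restarting, but dabrafenib is already interrupted at that temperature, so the added delay is at most the laboratory turnaround. If the sponsor regards Section 1.3 as outdated, the compulsory sample in uncomplicated fever is also new, including in unrelated infections; the dosing rules still justify it.
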